6.6 Record of Treatment Details and Acute Reactions (Form C)

The treatment details of TACE, SBRT and Avelumab will be documented. The incidence of acute toxicities \geq grade 3 by Common Toxicity Criteria for Adverse Events version 4.0 (CTCAE-v4) will also be recorded.

7. FOLLOW UP AND OUTCOME EVALUATION

7.1 Follow-Up Schedule

All participants will be followed every 2 weeks during the intervention. At each visit, patient's performance status and toxicity of treatment will be monitored, and blood test will be checked for complete blood picture, liver function, renal function, clotting profile and alpha-fetoprotein (AFP). A urine or serum pregnancy test needs to be performed at least every month while the subject is on avelumab therapy. Free T4 and TSH must be performed at least every 8 weeks during avelumab treatment and at end of treatment or 30 days post-treatment safety follow-up (if not performed in the previous 8 weeks). Upon completion of intervention, patients will be seen at least every 4 months in the first two years, and then every 6 months.

Blood-borne immune markers will be checked every 4 weeks for the first 24 weeks.

Extended safety follow-up:

- *Given the potential risk for delayed immune-related toxicities, safety follow-up must be performed up to 90 days after the last dose of avelumab administration.*
- *The extended safety follow-up beyond 30 days after last avelumab administration may be performed either via a site visit or via a telephone call with subsequent site visit requested in case any concerns noted during the telephone call.*

Treatment response and operability will be evaluated by contrast CT or MRI every 3 months during treatment, every 4 months in the first and second year after treatment, then every 6 months. All CT or MRI reporting will be according to Modified Response Evaluation Criteria for Solid Tumours (mRECIST) criteria.

European Organization for Research and Treatment of Cancer Quality of Life Questionnaire Core-30 (QLQ-C30) and Functional Assessment of Cancer Therapy-Hepatobiliary (FACT-Hep) questionnaires will be used for assessment of quality of life every 3 months in the first two years, then every 6 months.

7.2 Decision on Resectability, Subsequent Treatment and Treatment Failure

A multidisciplinary meeting consists of surgeons, oncologists, and radiologists will be held every 3 months to evaluate treatment response/failure, to decide on subsequent treatment.

Successful downstage and disease control (as defined by complete response, partial response and stable disease) will be evaluated for resection or transplantation of HCC

UCSF Criteria will be used to determine the suitability of transplantation

- Single tumor $\leq 6.5\text{cm}$
- Or up to 3 tumors $\leq 4.5\text{cm}$, and total sum is 8cm
- No vascular invasion

Treatment failure can be due to either poor liver function or tumor progression

Poor liver function is defined as

- Hepatic encephalopathy,
- Diuretic refractory ascites,
- Variceal bleeding,
- Bilirubin $>50\text{umol/L}$,
- Prothrombin time $>4\text{sec}$, or
- Child Pugh C status.

Tumor progression is defined as

- Extra-hepatic disease,
- New onset major vascular invasion (portal vein or hepatic vein invasion),
- Progressive disease according to mRECIST,

In patients who have treatment failure, unacceptable toxicity, or they have reached the end of treatment. Subsequent treatment will be decided in multidisciplinary panel based on best interests of patients. There is no restriction on choice of subsequent treatment.

7.3 Outcome Measures

7.3.1 Primary Endpoint

- Number of patients amenable to curative surgical interventions is defined as number of patients receiving curative surgical resection or transplantation after successful down-sizing of tumor(s) by intervention

7.3.2 Secondary Endpoints

- Response rate measured by mRECIST criteria:

Complete response (CR): Disappearance of any intra-tumoral arterial enhancement in all target lesions

Partial response (PR): At least a 30% decrease in the sum of diameters of viable (enhancement in the arterial phase) target lesions, taking as reference the baseline sum of the diameters of target lesions

Stable disease (SD): Any cases that do not qualify for either partial response or progressive disease

Progressive disease (PD): An increase of at least 20% in the sum of the diameters of viable (enhancing) target lesions, taking as reference the smallest sum of the diameters of viable (enhancing) target lesions recorded since treatment started

- Number of patients amenable to curative surgical interventions and/or achieve radiological complete response: defined as number of patients receiving curative surgical intervention or transplantation after successful downstaging (i.e. equivalent to primary endpoint) plus number of patients achieving radiological CR per mRECIST criteria. This endpoint is to reflect the number of patients achieve complete tumor clearance and potentially cure.
- Time to progression (TTP): measured from the date of first study treatment to radiographically documented progression according to mRECIST 1.1. This does not include death from any cause.
- Progression-free survival (PFS): measured from the date of first study treatment to radiographically documented progression according to mRECIST 1.1 or death from any cause (whichever occurs first). Participants alive and without disease progression or lost to follow-up will be censored at the date of their last radiographic assessment.
- Overall survival (OS): measured from date of first study treatment to the date of death from any cause. Participants alive or lost to follow-up will be censored at the date of their last visit.
- Quality of life (QoL): as assessed by the European Organization for Research and Treatment of Cancer Core Quality of Life Questionnaire (EORTC-QLQ-C30) and the Functional Assessment of Cancer Therapy–Hepatobiliary (FACT-Hep) questionnaires
- Safety outcome measures: Incidence, nature, and severity of adverse events graded according to the United States National Cancer Institute The Common Terminology Criteria for Adverse Events (NCI CTCAE 4.0)
- Pathological response: assessed as the percentage of surface with non-viable cancer cells (represented by necrosis or fibrosis, the ultimate stage of necrosis) in relation to the total tumor area and will be equal to: 100% – viable cancer cells (%). If there are

multiple tumors, the mean percentage will be used. Pathological complete response (pCR) is defined by the absence of viable tumor cells in any nodule.

- Disease control rate: Percentage of patients that had a CR, PR, or stable disease (SD) \geq 6 months per mRECIST
- Local control: defined as absence of recurrence within the high-dose region (80% isodose volume), demonstrated by new enhancement or mRECIST progressive disease
- Duration of response: time from first documented evidence of CR or PR until the first documented sign of disease progression (PD) or death from any cause
- Pattern of failure:
 - (1) In-field failure: defined as recurrence within the high-dose region (80% iso-dose volume), demonstrated by new enhancement or mRECIST progressive disease.
 - (2) Out-field (intra-hepatic): defined as new or mRECIST progressive disease within liver parenchyma, but outside the SBRT treated volume
 - (3) New vascular invasion: defined as new portal or hepatic vein invasion
 - (4) Distant failure: defined as new disease outside liver parenchyma
- Radiological response per RECIST 1.1

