1.2 TACE Plus SBRT

Further, meta-analysis has demonstrated TACE plus radiotherapy (RT) are more therapeutically beneficial than TACE alone. (14) There are several reasons for the potential synergism between the two treatment modalities: RT can kill the residual cancer cells after TACE, especially those at the tumor periphery that remain viable through the blood supply from the collateral circulation (15); secondly, TACE damages large numbers of cancer cells, which promotes the residual cells from a non-proliferative phase into cell proliferation, and thus become more radiosensitive (16); thirdly, TACE also decreases the tumor volume, which in turn reduces the radiation field and adverse events (17); in addition, the retention of chemotherapeutic agents from embolization in liver tumor cells has a radio-sensitizing effect

and accelerates tumor necrosis (18); finally, our group has reported the lipiodol enabled more accurate localization of HCC during SBRT. (19)

Our team had reviewed 73 intermediate to advanced stage HCC patients who received a single dose of TACE followed by SBRT. The median size of the tumor is 11.2cm, and 25% of them have the vascular invasion. The objective response rate (ORR) was 68%, the 1-year local control (LC) rate was 93.6%, the median progression-free survival (PFS) was 7.2 months, and median overall survival (OS) was 19.8 months. Twelve (16.4%) patients had treatment response were amendable for subsequent surgical resection, median OS was not yet reached for those who have operated. There was no patient developed radiation-induced liver disease (RILD) (20). Further, we also retrospectively compared the outcomes of TACE plus SBRT versus TACE in patients with intermediate HCC using propensity score matching (1:2). There was a significant improvement in median OS after TACE+SBRT when compared to TACE alone (23.9 months vs. 10.4 months, $p<0.001$). Also, there was a significant improvement of 3-year PFS (26.6% vs. 8.3%, $p=0.03$). (Unpublished data)

In a recently published phase II randomized trial, 90 unresectable HCC patients with vascular invasion were randomized to receive TACE+RT versus Sorafenib; the TACE+RT was associated with significantly better 12-week PFS rate (77.8% vs. 26.7%; $p<0.001$), median time to disease progression (30 weeks vs. 8 weeks; $p<0.001$), and median OS (55 weeks vs. 43 weeks; $p=0.04$) than Sorafenib alone. (21)

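### The progression definitions in sections 7.2 and 7.3.2 disagree; as printed, new disease outside the target lesions is not a progression event

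*Protocol*

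**What the plan says.** Section 7.3.2 prints its own response categories. PD is "An increase of at least 20% in the sum of the diameters of viable (enhancing) target lesions", measured from the smallest sum since treatment started. CR is "Disappearance of any intra-tumoral arterial enhancement in all target lesions". Neither rule has a clause for new lesions, non-target disease, vascular invasion or spread outside the liver.

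The time-to-event endpoints in the same section are:
- TTP: "measured from the date of first study treatment to radiographically documented progression according to mRECIST 1.1. This does not include death from any cause".
- PFS: "radiographically documented progression according to mRECIST 1.1 or death from any cause (whichever occurs first").
- Duration of response: from first CR or PR "until the first documented sign of disease progression (PD) or death from any cause".

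None of them refers to section 7.2. That section gives a wider meaning of tumor progression with three alternatives: extra-hepatic disease; "New onset major vascular invasion (portal vein or hepatic vein invasion"); and mRECIST PD. A new intra-hepatic lesion is not on the list.

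Under pattern of failure, 7.3.2 defines out-field failure as disease in the liver, outside the treated volume, that is either new or mRECIST PD. It also has separate categories for new vascular invasion and for distant failure. Objective 10 in section 2.2 asks for this pattern at the time of progression.

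**The concern.** The protocol uses at least three notions of progression that do not match, and the narrowest is the one printed beside the endpoints. Sections 7.2 and 7.3.2 both place new disease next to mRECIST PD, as if it lay outside it. A reader who follows the printed PD rule would not count a new lung metastasis, a new liver nodule or a new portal vein thrombus as progression while the target lesions are stable. A reader who follows the published criteria behind the name may count them.

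TTP, PFS, duration of response, CR and everything built on CR are at stake: the objective response rate and the composite of surgery and/or CR, which is meant to reflect complete tumor clearance. Stable disease is the residual category, so the disease control rate inherits the gap. Every error runs in favour of the treatment. Section 1.2 itself names distant control as the remaining challenge in this population.

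**Working it through.** **Side by side.** Take a patient whose target lesions are stable and who develops one new finding.

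| New finding | Printed PD rule, 7.3.2 | Tumor progression, 7.2 | Pattern of failure, 7.3.2 | Date listed for Form D, 7.4 |
|---|---|---|---|---|
| Liver lesion outside the treated volume | No | Not listed | Out-field failure | Yes |
| Portal or hepatic vein invasion | No | Yes | New vascular invasion | No |
| Disease outside the liver | No | Yes | Distant failure | Yes |

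Three of the four pattern-of-failure categories can therefore arise without meeting the printed PD rule, although objective 10 describes them at the time of progression. TTP excludes death, so such a patient might never have an event. PFS and duration of response count death, so the event would appear late. After curative resection or transplantation no target lesion is left to grow, so a recurrence cannot meet the printed rule either.

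**How many progressions are exposed.** The protocol gives no expected TTP or PFS for this trial, so there is no plan figure to reproduce. Section 1.2 describes a pilot of 73 patients given TACE then SBRT without avelumab, in which "the 1-year local control (LC) rate was 93.6%, the median progression-free survival (PFS) was 7.2 months" and median OS was 19.8 months. Assume constant hazards, and take local failure as a stand-in for target growth. That is reasonable because entry allows at most 3 lesions and no extra-hepatic metastases, and SBRT is given to all targets.

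1. PFS events by 12 months: 1 − exp(−ln 2 × 12/7.2) = 0.685.
2. Deaths by 12 months: 1 − exp(−ln 2 × 12/19.8) = 0.343.
3. Local failures by 12 months: 1 − 0.936 = 0.064.
4. In-field share if no death precedes progression: 0.064/0.685 = 9%.
5. In-field share if every death precedes progression: 0.064/(0.685 − 0.343) = 0.064/0.342 = 19%.

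Cross-check with monthly hazards: local −ln(0.936)/12 = 0.00551, PFS ln 2/7.2 = 0.09627, OS ln 2/19.8 = 0.03501. The local share of the progression hazard is 0.00551/0.09627 = 5.7%, or 0.00551/(0.09627 − 0.03501) = 9.0%. The 9% to 19% range is the more cautious of the two.

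**Effect on 12-month freedom from progression, same assumptions.**

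- Full definition: exp(−12 × 0.09627) = 31% if no death comes first; exp(−12 × 0.06126) = 48% if all deaths do.
- Printed rule, with no outside failure accompanied by target growth: 94%.
- Printed rule, with half of outside failures accompanied by target growth: exp(−12 × (0.00551 + 0.5 × 0.09076)) = 54%, or exp(−12 × (0.00551 + 0.5 × 0.05575)) = 67%.

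**Sample size.** The design in 8.2 (continue with at least 1 of 10, success with at least 4 of 29) has exact type I error 0.0468 and power 0.8011, and 29/0.9 = 32.2, rounded up to 33. No input involves progression, so it stands.

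**The case against.** The strongest reply is that TTP and PFS do not cite the printed list. They cite mRECIST by name, and section 7.1 says all CT and MRI reporting follows it. Assessors may therefore apply the full published criteria, which are not at hand here. The separate items in 7.2 could be clarifying redundancy. Indeed, unless mRECIST PD is meant to cover new liver lesions, 7.2 would not count one as treatment failure, which is implausible. Objective 10 also makes sense only if such failures count as progression.

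This stands to the extent that the text does not prove the investigators intend the narrow reading. It does not remove the conflict: the out-field definition sets new disease against mRECIST PD, the printed rule is the only one the document spells out, and the label "radiographically documented progression according to mRECIST 1.1" does not say which rule governs.

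Two stronger readings are tempting. One is that all three time-to-event endpoints are blind to distant failure. They are not: PFS and duration of response include death, and only TTP could lose the event altogether. The other is that only 9% of first-year progressions are in-field. That is the low end, because its denominator treats every PFS event as a progression.

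It is also fair that the pilot's definitions of PFS and local control are not given, that the entry limits restrict baseline non-target disease, and that an SAP may set the rule for recurrence after surgery.

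**Conclusion.** The protocol contradicts itself on what counts as progression, and its printed PD and CR rules, if followed, give estimates that favour the treatment. TTP could miss new liver, vascular or distant disease; PFS and duration of response would register it late; CR could coexist with it.

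The size is illustrative. With about 9% to 19% of first-year progressions in-field, most would be exposed to the gap. That rests on constant hazards, on local failure as a stand-in for target growth, and on a pilot without avelumab. The contradiction in the text does not depend on it.

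The affected endpoints are secondary ones in a single-arm trial. The primary endpoint counts patients who receive curative surgery, so it and the 4-of-29 rule are untouched. The point should be corrected, but it does not threaten the main conclusion.

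**What to change.** State one endpoint definition of progression in 7.3.2: any of target growth of at least 20% from the smallest sum, a new intra-hepatic lesion, new portal or hepatic vein invasion, extra-hepatic disease, or recurrence after resection or transplantation. Cite it in TTP, PFS and duration of response, and reconcile the list in 7.2 with it. What 7.2 should imply for a patient's treatment is a separate matter for the clinical team.

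Require for CR that no non-target or new viable disease is present. Replace mRECIST 1.1 by mRECIST; response by RECIST 1.1 is already its own endpoint. Add a date for new vascular invasion to Form D, because section 7.4 lists dates only for in-field, out-of-field and distant failure.

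The cost is protocol wording and one form field. Section 8.1 calls for an amendment if key secondary endpoints change after the study has begun. PFS, TTP and CR may look less favourable. The sample size does not change.

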2.2 Secondary Objectives

1. To assess the number of patients amenable to curative surgical interventions and/or achieve radiological complete response in HCC patients treated with combined TACE and SBRT followed by Avelumab
2. To assess the objective response rate in HCC patients per mRECIST treated with combined TACE and SBRT followed by Avelumab
3. To evaluate the time-to-progression (TTP), progression-free survival (PFS) and overall survival (OS) in HCC patients treated with combined TACE and SBRT followed by Avelumab
4. To measure the toxicities in HCC patients treated with combined TACE and SBRT followed by Avelumab
5. To evaluate the patient-reported quality of life (QoL) treated with combined TACE and SBRT followed by Avelumab
6. To describe the pathological response among HCC patients amenable to surgery after receiving combined TACE and SBRT followed by Avelumab
7. To assess the disease control rate (DCR) in HCC patients treated with combined TACE and SBRT followed by Avelumab
8. To assess the local control rate among HCC patients treated with combined TACE and SBRT followed by Avelumab
9. To evaluate the duration of response among HCC patients responded to combined TACE and SBRT followed by Avelumab
10. To describe the pattern of failure at the time of progression

11. To assess the objective response rate in HCC patients per RECIST 1.1 treated with combined TACE and SBRT followed by Avelumab
12. Collection of bio-specimens for future correlative studies in patients treated with TACE and SBRT followed by Avelumab

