8. STATISTICS

8.1 Statistical Analysis

- Patients who complete TACE will be considered as the study population for primary and secondary endpoints.
- The primary endpoint - the rate of patients amendable to curative surgical intervention will be estimated based on exact binomial distribution.

- Objective response rate (ORR), pathological response rate, and number of patients amendable to curative interventions and / or radiological CR will be expressed based on exact binomial distribution.
- Survival outcomes, including TTP, PFS and OS and their corresponding 95% confidence interval, will be estimated using Kaplan-Meier method.
- Patient reported QoL scores will be estimated at baseline, during and following therapy. Scores at each time point will be summarized with descriptive statistics including means, standard deviations, median and range. The changes from baseline during therapy and after therapy will be calculated for each patient and also summarized with means and standard deviations/95% CI. Linear mixed-effect model will be used to study the longitudinal changes of QoL scores.
- All of the tests and reported P values will be 2-tailed, and P<0.05 will be considered statistically significant. The analyses will be performed using statistical software packages SPSS and R.

Procedures for Handling Missing, Unused, and Spurious Data: All available data will be included in the data listings and tabulations. Where appropriate, imputations of values for missing data for primary and secondary efficacy analyses will be performed as specified in the Statistical Analysis Plan. All data recorded on the CRF will be included in the data listings that will accompany the clinical study report.

If, after the study has begun, but prior to the conduct of any analysis, changes made to primary and / or key secondary endpoints, or the statistical methods related to those hypotheses, then the protocol will be amended. Changes to exploratory analyses made after the protocol finalized will be documented and referenced in the final report. Post hoc exploratory analyses will also be identified in the final report.

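### The surgery-and/or-complete-response endpoint is defined as a sum of two counts, so a patient who meets both parts could be counted twice

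*Protocol*

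**What the plan says.** Four places in the Protocol describe this endpoint as a number of patients who meet one condition or the other:

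- The objective in section 2.2: "To assess the number of patients amenable to curative surgical interventions and/or achieve radiological complete response".
- The endpoint's label in section 7.3.2: "Number of patients amenable to curative surgical interventions and/or achieve radiological complete response".
- The purpose sentence in the same bullet: "This endpoint is to reflect the number of patients achieve complete tumor clearance and potentially cure".
- The analysis line in section 8.1: "number of patients amendable to curative interventions and / or radiological CR will be expressed based on exact binomial distribution".

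The definition in section 7.3.2 reads differently. Its first term is the count of patients receiving curative surgery or transplantation after downstaging, glossed as "i.e. equivalent to primary endpoint". Its second term is "plus number of patients achieving radiological CR per mRECIST criteria". The second term is not limited to CR without surgery, and nothing says that a patient is counted once.

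Two further places matter. Section 7.2 states which patients are considered for surgery: those with disease control, "as defined by complete response, partial response and stable disease) will be evaluated for resection or transplantation of HCC". Section 8.1 fixes the denominator: "Patients who complete TACE will be considered as the study population for primary and secondary endpoints".

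**The concern.** The label and the definition describe two different quantities. The label is a union: a patient qualifies by either route and counts once. The definition is a sum of two counts. They agree only if no operated patient also had a radiological CR, and nothing in the protocol makes the two groups mutually exclusive.

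The protocol presents this endpoint as its measure of potential cure. In a single-arm trial of about 30 patients, a few double-counted patients would visibly raise that rate. The exact binomial also needs a yes/no outcome per patient. A literal sum lets a patient score 0, 1 or 2.

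**Working it through.** **Notation.** Let S be the number operated, C the number with CR, B the number with both, and N the number analysed.

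- Definition as written: S + C.
- Endpoint as labelled: S + C − B.
- Overstatement if the definition is applied literally: B/N.

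**Can B exceed zero?** Section 7.2 includes complete response among the states that lead to evaluation for resection or transplantation. Section 7.1 has response and operability assessed by the same imaging, every 3 months during treatment. A CR can therefore be recorded before an operation. Evaluation is not surgery, so B may also be zero.

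**Figures in the plan.** The protocol gives no expected value for this endpoint, no CR rate and no overlap. The only design figures belong to the primary endpoint (section 8.2): 5% against 20%, continue with at least 1 of 10, success with at least 4 of 29. These reproduce, with exact type I error 0.0468, power 0.801, and 29/0.9 = 32.2, rounded up to 33. None of them uses the composite.

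**Illustration 1 (assumed rates).** Take N = 29, the two-stage total. Assume 20% operated (0.20 × 29 = 5.8, so S = 6) and 25% with CR (0.25 × 29 = 7.25, so C = 7). The sum is 6 + 7 = 13, or 13/29 = 44.8% (Clopper-Pearson 95% interval 26.4 to 64.3), whatever the overlap.

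| B | Each patient counted once | Rate (95% interval) | Overstatement by the sum |
|---|---|---|---|
| 0 | 13/29 | 44.8% (26.4–64.3) | 0 points |
| 3 | 10/29 | 34.5% (17.9–54.3) | 3/29 = 10.3 points |
| 6 | 7/29 | 24.1% (10.3–43.5) | 6/29 = 20.7 points |

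Each double-counted patient adds 1/29 = 3.4 points.

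**Illustration 2 (full accrual).** Take N = 33, the most that the section 8.1 population could contain, and assume S = 4 and C = 8. The sum is 12/33 = 36.4% (20.4–54.9). Counted once, the result is 12/33 = 36.4% if B = 0, 10/33 = 30.3% (15.6–48.7) if B = 2, and 8/33 = 24.2% (11.1–42.3) if B = 4. The overstatement is 0 to 12.1 points, at 1/33 = 3.0 points per patient.

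**Does the exact binomial fit?** Write s, c and b for the rates of surgery, CR and both. The per-patient variance of the sum is (s + c)(1 − s − c) + 2b. The binomial variance is the first term alone. With s = 0.20 and c = 0.25, the binomial value is 0.45 × 0.55 = 0.2475. The sum has variance 0.2475 at b = 0, 0.4475 at b = 0.10 and 0.6475 at b = 0.20. The binomial therefore misfits the sum as soon as b is above zero. It is exact for the union at any overlap, because each patient is then scored 0 or 1.

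**The case against.** The strongest reply is that the intent is plain. The objective, the label, the purpose sentence and the analysis line all describe a number of patients, and a patient cleared by both routes is still one patient. On that reading *plus* merely lists the two qualifying groups, and the exact binomial is the right method. This stands as an account of intent. It does not remove the conflict, because the sentence that formally defines the endpoint states an addition. An analyst who followed it faithfully would add the counts.

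It can also be said that counting rules for composites often sit in a statistical analysis plan, which is not at hand. But this is not a detail left open: the protocol fixes the rule, and fixes it in a form that contradicts the rest of the text.

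Three stronger readings are tempting and are not supported:

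- A reader might infer that double counting will occur, or that the two groups overlap by design. Section 7.2 speaks only of evaluation, and no section requires complete responders to be operated on.
- A reader might conclude that the exact binomial is the wrong method. It is correct for the and/or count and fails only for a literal sum with overlap.
- A reader might stress that the sum can exceed the number of patients. That is arithmetically possible but remote: at the 20% surgery rate of section 8.2, the CR rate would have to be above 80%.

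The consequences are also limited. Section 8 attaches no hypothesis, threshold or decision to this endpoint, and surgery and mRECIST response are each listed as endpoints in their own right.

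**Conclusion.** The concern holds as a contradiction between a secondary endpoint's and/or label and its additive definition. The harm is conditional: it needs the definition to be applied as written and at least one patient to have both surgery and CR. In that case the potential-cure rate is overstated by B/N and the planned exact interval is computed on a total that is not binomial.

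Under the assumed 20% surgery and 25% CR in 29 patients, the overstatement ranges from 0 to about 20 points. The rates, the overlap and the use of 29 as denominator are assumptions for illustration, not protocol figures. The primary endpoint, the sample size, the two-stage rule and the toxicity stopping rule do not depend on this endpoint.

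**What to change.** In section 7.3.2, replace the additive definition with: the number of patients who received curative resection or transplantation after successful downstaging, or who achieved radiological CR per mRECIST, or both, each patient counted once. In section 8.1, apply the exact binomial to that count, over the population already stated there (patients who complete TACE). Reporting the number who met both parts alongside would make the result easy to check.

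The cost is one sentence, settled before any analysis. No clinical rule, sample size or decision boundary changes. The only downside is that the reported rate may be lower than the sum would have given.

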7.4 Follow-Up and Record of Events (Form D)

- The patient should be followed-up until death.
- The dates of diagnosis of in-field, out-of-field (intra-hepatic), and distant failure should be recorded.
 - In-field failure: defined as recurrence within the high-dose region (80% iso-dose volume), demonstrated by new enhancement or mRECIST progressive disease.
 - Out-field (intra-hepatic): defined as new or mRECIST progressive disease within liver parenchyma, but outside the SBRT treated volume
 - Distant failure: defined as new disease outside liver parenchyma
- The incidence of late toxicities \geq grade 3 by Common Toxicity Criteria for Adverse Events version 4.0 (CTCAE-v4) should be recorded.
- All causes of death (if occur) will be recorded. Deaths due to unknown cause are counted as deaths due to HCC if disease is still present at last assessment.

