7.5 Criteria for Removal From Protocol Treatment

- Disease progression
- Inter-current disease that would affect assessments of clinical status to a significant degree, require discontinuation of drug, or both
- Unacceptable toxicity
- The patient may withdraw from treatment at any time for any reason. The reason should be recorded. Follow-up will be continued for all consenting patients per standard clinical procedures, including regular follow-up visits, clinical and laboratory assessments for up to 5 years

- Avelumab treatment for maximum of 2 years

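### Overall survival counts deaths whenever they occur but censors living patients at their last visit, which biases Kaplan-Meier survival downward if the data are cut early

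*Protocol*

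**What the plan says.** Section 7.3.2 defines OS as "measured from date of first study treatment to the date of death from any cause". For everyone else it states: "Participants alive or lost to follow-up will be censored at the date of their last visit". No OS data cut-off or last-known-alive date is given.

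Section 7.4 adds "The patient should be followed-up until death" and requires all causes of death to be recorded, so deaths are not tied to the visit calendar.

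Section 7.1 sets the calendar. On treatment: "All participants will be followed every 2 weeks during the intervention". Afterwards: "Upon completion of intervention, patients will be seen at least every 4 months in the first two years, and then every 6 months". Section 7.5 limits the intensive phase: "Avelumab treatment for maximum of 2 years". Section 7.1 also treats a visit and a telephone contact as different things, since late safety follow-up "may be performed either via a site visit or via a telephone call". Section 8.1 estimates OS by Kaplan-Meier with a 95% confidence interval.

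**The concern.** Take two patients with the same last visit. One dies three months later: those months stay in the analysis and end in an event. The other is known to be alive at the data cut: those three months are removed. Whether time after the last visit enters the risk set thus depends on whether the patient died. Kaplan-Meier assumes that censoring carries no such information.

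The result is an OS curve that is too low for a reason unrelated to treatment. Sampling error is random and shows in the confidence interval; this error goes one way and does not. The rule is written into the endpoint definition, so it has not been left open for an analysis plan to settle.

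**Working it through.** **The plan's own figure.** The protocol gives no sample size, event count or power for OS. Its only design figure is the accrual of 33 for the primary endpoint, and that reproduces. Continuing with at least 1 of 10 and succeeding with at least 4 of 29 gives a type I error of 0.047 and power of 0.801 at 5% versus 20%, and 29/0.9 = 32.2, rounded up to 33. The check below uses n = 33 for sampling error.

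**Direction.** Kaplan-Meier is S(t) = Π(1 − d/n) over the death times, with d deaths among n at risk. Under the last-visit rule d is unchanged. At each death time, however, n falls by m, the number of patients alive at that point whose last visit has already passed. Since 1 − d/(n − m) ≤ 1 − d/n, every factor is equal or smaller. If all deaths up to the cut are captured, the rule can only lower the curve.

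**Inputs for the size.**
- From the protocol: visits every 2 weeks on treatment, then every 4 months for two years, then every 6 months (section 7.1); at most 2 years of avelumab (section 7.5); median OS of 19.8 months in the institution's TACE plus SBRT series (section 1.2).
- Assumed, because the protocol gives no figure: exponential survival; uniform accrual over 24 or 36 months; minimum follow-up of 6, 12 or 24 months at the data cut; 2, 6, 12 or 24 months on treatment; every death before the cut captured at its date.

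True 24-month OS is exp(−ln 2 × 24/19.8) = 43.2%.

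**Simulation.** There were 400,000 patients per scenario. Survivors were censored either at the cut-off or at the last scheduled visit. Results for 6 months on treatment:

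| Accrual (months) | Minimum follow-up (months) | Shift in 24-month OS (points) | Median under last-visit rule (months) |
|---|---|---|---|
| 24 | 6 | −5.3 | 18.2 |
| 24 | 12 | −2.6 | 18.9 |
| 24 | 24 | −0.3 | unchanged |
| 36 | 6 | −2.3 | 18.8 |
| 36 | 12 | −1.4 | 19.2 |
| 36 | 24 | −0.2 | unchanged |

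Censoring at the cut-off returns the true values: median 19.8 months, 24-month OS 43%. With 12 months on treatment and 24 months' accrual, the shift is −3.9 points at 6 months' minimum follow-up and −2.2 at 12. If every patient stays on 2-weekly visits for 24 months, it is 0 to −0.7 points in all scenarios.

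**Hand check (accrual 24, minimum 12).** In the simulation 56% die before the cut, and each survivor loses 2.24 months on average.
- Hazard: ln 2/19.8 = 0.0350 per month.
- Person-time per patient: 0.56/0.0350 = 16.0 months.
- Time dropped: 0.44 × 2.24 = 0.99 months.
- Inflated hazard: 0.0350 × 16.0/(16.0 − 0.99) = 0.0373.
- 24-month OS: exp(−0.0373 × 24) = 40.9%, or 2.3 points low, close to the simulated 2.6.

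**Against sampling error.** In 4,000 simulated trials of 33 patients (6 months on treatment, accrual 24 months), the mean shift at 24 months was −2.6 points against an SD of 9.7 with 12 months' minimum follow-up. With 6 months it was −5.2 points against an SD of 11.9. The estimated median fell by 0.8 and 1.1 months on average.

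**The case against.** The strongest reply is that the size rests on an early data cut that the protocol never states. Following patients until death suggests long follow-up, and with 24 months' minimum follow-up the shift at 24 months is 0.3 points or less. That stands. A reader might infer that OS will be too low whenever it is analysed; the documents do not support this, because the effect at 24 months nearly vanishes with mature data.

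The visit gaps are also upper limits. Section 7.1 says at least every 4 months, and quality of life is collected every 3 months in the first two years. With 3-month gaps and 12 months' minimum follow-up, 24-month OS is 41.4% against 43.1%, so the bias is smaller but still present.

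The protocol does not say how deaths between visits become known. Section 7.4 implies that they are captured; any that are missed would offset the bias. For a patient who is truly lost, the last visit may already be the last date known alive, and the rule then costs nothing.

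A reader might also infer that the rule distorts comparison with the historical series in section 1.2. The documents do not support that either. No OS comparison is planned, the historical hypothesis in section 8.2 concerns the surgery rate, and the censoring rule of the cited series is not given.

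**Conclusion.** The point holds as a minor one. The stated rule makes censoring depend on outcome, and its effect on Kaplan-Meier OS is downward. With a 19.8-month median and 24 to 36 months' accrual, 24-month OS is about 2 to 5 points low at 6 months' minimum follow-up and 1 to 3 points low at 12 months. It is near zero at 24 months or more, or while patients remain on 2-weekly visits. The median is 0 to about 1.6 months short.

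These sizes rest on assumed accrual, follow-up, treatment duration and exponential survival, and on complete capture of deaths. The bias is below the sampling error at n = 33. OS is a secondary endpoint that is estimated without a formal test, so the primary endpoint, the two-stage design and the toxicity stopping rule are untouched. It merits correction because it is avoidable, goes one way and is not reflected in the confidence interval.

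**What to change.** Replace the OS censoring sentence in section 7.3.2 with a rule in three parts:

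1. Set a common data cut-off date for OS.
2. Confirm the vital status of every patient at that date by record check or telephone, and censor those confirmed alive at the cut-off.
3. Censor only patients whose status cannot be confirmed, at the last date known alive from any source.

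The second part does the work. Censoring everyone at the last contact date, without the check at cut-off, would keep the same asymmetry wherever contacts are sparse.

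The cost is a short wording change and a small amount of tracing at the data cut for at most 33 patients. It needs no extra visits or patients.
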